6.2. Background Characteristics

6.2.1. Participant Disposition

The number and percentage of participants in the following categories (analysis sets defined in Section 5) will be summarized by treatment group as defined in Section 6.1 based on Randomized Set:

- Randomized Set
- Full Analysis Set
- Per-protocol Set
- Safety Set
- Solicited Safety Set
 - Day 1 Solicited Safety Set
 - Day 22 Solicited Safety Set

The percentages will be based on the number of participants in the Randomized Set (as randomized), except that for the Safety Set and Solicited Safety Set in which the percentages will be based on the number of participants in the Safety Set (as treated).

The number of participants in the following categories will be summarized based on participants screened:

- Number of participants screened
- Number and percentage of screen failure participants and the reason for screen failure

The percentage of participants who screen failed will be based on the number of participants screened. The percentage of participants reporting each reason for screen failure will be based on the number of participants who screen failed.

The number and percentage of participants in each of the following disposition categories will be summarized by treatment group based on the Randomized Set:

- Received Day 1 injection
- Received Day 22 injection
- Prematurely discontinued before receiving the Day 22 injection and the reason for discontinuation
- Completed the study
- Prematurely discontinued the study and the reason for discontinuation

The number and percentage of participants by IRT randomized stratum (65 to <75 years and ≥75 years) will be presented by treatment group. Also, the concordance between IRT randomized stratum and CRF derived stratum will be tabulated by treatment group.

A participant disposition listing will be provided, including informed consent, participants who completed the study injection schedule, participants who completed study, participants who discontinued from study vaccine or who discontinued from participation in the study, with reasons for discontinuation. A separate listing will be provided for screen failure participants with reasons for screen failure.

A participant, who has completed all periods of the study, including the last visit or scheduled procedure (i.e., 6 months after administration of the Day 22 injection), is considered to have completed the study.

6.2.2. Demographics and Baseline Characteristics

Descriptive statistics will be calculated for the following continuous demographic and baseline characteristics:

- Age (years)
- Weight (kg)
- Height (cm)
- Body mass index (BMI) (kg/m²)

The number and percentage of participants will be provided for following categorical variables:

- Randomized age group (65 to <75 years, ≥75 years)
- Actual age group (65 to <75 years, \ge 75 years)
- Gender (Male, Female)

- Race (White, Black or African American, Asian, American Indian or Alaska Native, Native Hawaiian or Other Pacific Islander, Other, Not Reported, Unknown)
- Ethnicity (Hispanic or Latino, Not Hispanic or Latino, Not Reported, Unknown)

The summaries will be presented by treatment group as defined in Section 6.1. The summaries will be provided separately based on the Randomized Set, FAS, Safety Set, and PP Set.

For screened failure participants, age (years), as well as gender, race, ethnicity will be presented in a listing.

In addition, participants with any inclusion and exclusion criteria violation will also be provided in a listing.

6.2.3. Medical History

Medical history data will be coded by system organ class (SOC), high level group term (HLGT) (for selected medical conditions), and preferred term (PT) according to the Medical Dictionary for Regulatory Activities (MedDRA, version 25.0 or higher).

The number and percentage of participants with any medical history will be summarized by SOC and PT based on the Safety Set. A participant will be counted only once for multiple events within each SOC and PT. SOC will be displayed in internationally agreed order. PT will be displayed in descending order of frequency of the "D1: Fluzone HD+mRNA-1345 (µg) and D22: placebo" group and then alphabetically within SOC.

Number of events and number of participants with selected medical conditions of clinical interest, as indicated in Appendix I, will also be summarized by SOC, HLGT, and PT for each treatment group.

Medical history data and selected medical conditions of clinical interest will be presented in a listing separately.

6.2.4. Prior and Concomitant Medications

Any medication or vaccine (including OTC or prescription medicines, recreational drugs, vitamins, and/or herbal supplements) or other specific categories of interest that the participant is receiving at the time of enrollment or receives during the study will be recorded in the participant's eCRF. Specific categories of interest are detailed in the section 6.9 of the study protocol.

Prior and concomitant medications will be coded using the World Health Organization (WHO) drug dictionary (WHO-DD). The summary of concomitant medications will be based on the Safety Set. Imputation rules for missing/partial dates for medications is detailed in Appendix C.

For analysis purpose, a medication taken prior to the Day 1 injection date, regardless of whether the end date is before or after the injection date, is defined as "prior"; if the medication is taken on or after the Day 1 injection date through Month 6/EoS visit, then it is considered "concomitant", regardless of whether the start date is before or after the injection date.

An overall summary table of concomitant medications and non-study vaccinations will be provided to present the number and percentage of participants who take the following:

- Any concomitant medications and non-study vaccinations within 7 days post any injection
- Any concomitant medications and non-study vaccinations within 21 days post any injection
- Any non-study vaccinations within 7 days post any injection
- Any non-study vaccinations within 21 days post any injection
- Any prophylactic antipyretics or analgesics medication within 21 days post any injection
- Any antipyretic or analgesic medication within 21 days post any injection

A summary table of concomitant medications and non-study vaccinations within 21 days post any injection will be provided by ATC level 2 and PT. PT will be displayed in descending order of frequency of the "D1: Fluzone HD+mRNA-1345 (µg) and D22: placebo" group. A separate summary table of non-study vaccinations within 7 days post any injection will be also provided by PT.

An overall summary of medications taken to prevent or treat fever or pain within 7 days post each injection will be also provided by treatment group based on Day 1 (Day 22) Solicited Safety Set. The summary will be based on participants' responses to the eDiary questions regarding whether they have taken any antipyretic or analgesic medications to prevent or treat fever/pain within 7 days post injection.

Prior, concomitant and non-study vaccinations will be presented in a listing.

6.2.5. Concomitant Procedures/Surgeries

Procedures and/or surgeries data will be coded by SOC and PT using the MedDRA. Imputation rules for missing/partial dates of procedures/surgeries are detailed in Appendix D.

For analysis purpose, a procedure/surgery occurred prior to the injection date (including cases where the procedure/surgery date is completely missing) is defined "prior"; if the procedure/surgery is performed on or after the Day 1 injection date through Month 6/EoS visit, then it is considered "concomitant".

The number and percentage of participants with any concomitant procedure/surgery within 21 days post any injection will be summarized by SOC and PT based on the Safety Set. A participant will be counted only once for multiple procedures/surgeries within each SOC and PT. SOC will be displayed in internationally agreed order. PT will be displayed in descending order of frequency of the "D1: Fluzone HD+mRNA-1345 (µg) and D22: placebo" group and then alphabetically within SOC.

Concomitant procedures/surgeries will be presented in a listing.

6.2.6. Study Exposure

The number and percentage of participants received vaccine injection at Day 1 visit, Day 22 visit as well as the study duration from the Day 1 injection to the EoS will be summarized by treatment group and overall for Safety Set and PP Set. Study injection detail as well as participant with dosing error will be presented in a listing.

6.2.7. Important Protocol Deviations

Important protocol deviations are a subset of protocol deviations that may significantly impact the completeness, accuracy, and/or reliability of the study data or that may significantly affect a participant's rights, safety, or well-being. Important protocol deviations will be identified based on the protocol at the start of the study and updated during the conduct of the study, and will be finalized before database lock (DBL).

The number and percentage of the participants with any important protocol deviations in each category will be provided by treatment group based on the Randomized Set.

A subset of important protocol deviations, which impact critical or key study data and thus lead to exclusion of participants from the PP set, may include (but are not limited to) the following:

- Received a wrong Day 1 study intervention or Day 22 study intervention
- Enrolled/dosed at two investigational sites
- Did not have a baseline immunogenicity assessment
- Did not have any postinjection immunogenicity assessment
- Received prohibited medication (s) affecting immune responses

The important protocol deviations leading to exclusion from the PP set will be determined and documented by Sponsor prior to DBL and unblinding. Reasons of exclusion from PP Set for immunogenicity will be summarized by treatment group.

Significant protocol deviations will be presented in a listing.

6.2.8. COVID-19 Impact

An individual data listing on COVID-19 impact will be provided for the Randomized Set and it will include which visit(s)/assessment(s) has (have) been missed due to COVID-19, along with the specific relationship to COVID-19.

6.3. Safety Analysis

Safety and reactogenicity will be assessed by clinical review of all relevant parameters including solicited ARs (local and systemic), unsolicited AEs, SAEs, MAAEs, AESI, AEs leading to withdrawal from study vaccine and/or study participation, vital signs, and physical examination findings. Solicited ARs will be coded according to the MedDRA for AR terminology and unsolicited AEs will be coded by SOC and PT according to the MedDRA (version 25.0 or higher). The Toxicity Grading Scale for Healthy Adult and Adolescent Volunteers Enrolled in Preventative Vaccine Clinical Trials (DHHS 2007) will be used in this study.

All safety analyses will be based on the Safety Set, except summaries of solicited ARs, which will be based on the Solicited Safety Set. All safety analyses will be provided by treatment group as defined in Section 6.1, unless otherwise specified.

6.3.1. Solicited Adverse Reactions

An AR is any AE for which there is a reasonable possibility that the test product caused the AE. The term "Solicited Adverse Reactions" refers to selected signs and symptoms occurring after each injection administration during a specified post-injection follow-up period (day of injection and 6 subsequent days). The solicited ARs are recorded by the participant in eDiary. The eDiary will solicit daily participant reporting of ARs using a structured checklist (Section 8.3.3 of the study protocol). Participants will record such occurrences in an eDiary from Day 1 through Day 7 (i.e., the day of injection and 6 subsequent days). Local solicited ARs will be recorded separately for each injection site (left and right arm). Severity grading of reactogenicity will occur automatically based on participant entry in the eDiary according to the grading scales presented in Table 7 of the study protocol, which are modified from the toxicity grading scale for healthy adult and adolescent volunteers enrolled in preventive vaccine clinical trials (DHHS 2007). All solicited ARs (local and systemic) reported in the eDiary will be considered causally related to study injection.

If a participant had a Grade 1 or higher AR during the solicited period and did not record the event in the eDiary, the event should be recorded on the Reactogenicity eCRF. If the event starts during the solicited period, but continues beyond 7 days after dosing, the participants should notify the site to provide an end date and close out the event on the Reactogenicity eCRF. If the participant reported an event that started after the solicited period (i.e., beyond 7 days after

dosing), it should be recorded as an AE on the AE eCRF. Causality for these events will be determined per assessment by the Investigator.

The following local ARs for each injection site (left and right arm) will be solicited by the eDiary: injection site pain, injection site erythema (redness), injection site swelling/induration (hardness), and axillary (underarm) swelling or tenderness ipsilateral to the injection arm. The following systemic ARs will be solicited by the eDiary: headache, fatigue, myalgia (muscle aches all over the body), arthralgia (aches in several joints), nausea/vomiting, chills, and fever.

All analyses of solicited ARs will be provided separately after Day 1 injection and Day 22injection by treatment group as defined in Section 6.1 based on the Day 1 (Day 22) Solicited Safety Set. Summaries of local solicited ARs will be also presented by treatment group and injection content (mRAN-1345, Fluzone HD, and Placebo).

The number and percentage of participants with any solicited ARs, any solicited local ARs and any solicited systemic ARs during the 7-day follow-up period after each injection will be summarized by treatment group with a 2-sided 95% exact CI using the Clopper-Pearson method. Refer to Safety Estimand 3a in Appendix G, Table 6.

The following summaries for solicited ARs will be presented by treatment group:

- The number and percentage of participants who reported any solicited ARs, any solicited local ARs and any solicited systemic ARs within 30 minutes after each injection.
- The number and percentage of participants who reported each individual solicited AR (has a severity grade of Grade 1 or greater) during the 7-day follow-up period after each injection will be summarized by severity grade. For each local solicited AR after Day 1 injection, the summary will be based on the highest grade of the ARs observed from both injection sites (left and right arm).
- The number and percentage of participants who reported each individual solicited AR will be summarized by the onset day relative to the corresponding injection (Day 1 through Day 7). The onset day of an individual solicited AR is defined as the time point after each injection at which the respective solicited AR first occurred. For each local solicited AR after Day 1 injection, the summary will be based on the earliest onset day of the ARs from both injection sites (left and right arm).
- The duration (days) of each individual solicited AR will be summarized descriptively for each injection. The duration will be calculated as: end date of solicited AR event reaction start date of solicited AR event +1, no matter if it is intermittent or continued or if the solicited AR continues beyond 7 days. For each local solicited AR after Day 1

injection, the summary will be based on the longest duration of the ARs observed from both injection sites (left and right arm).

• The number and percentage of participants who reported each individual solicited AR that continue beyond 7 days post-injection will be summarized for each injection.

The number and percentage of participants who reported each individual solicited AR after each injection summarized by severity grade and by onset day will be also presented separately for local solicited ARs only by treatment group and injection content.

Bar plots may be created to display the percentage of participants who reported solicited AR after each injection.

The summaries of solicited ARs by treatment group and local solicited ARs by treatment group and injection content may be provided for the following subgroup:

- Age group (65 to <75 years, \ge 75 years)
- Sex (Male, Female)
- Race (White, Black, Asian, Other [including American Indian or Alaska Native, Native Hawaiian or other Pacific Islander and other races])
- Ethnicity (Hispanic or Latino, Not Hispanic or Latino)

These summaries may be provided for additional subgroups of selected baseline characteristics. If the number of participants in certain subgroups are too small, it may be combined with the other subgroups for the subgroup analyses.

6.3.2. Adverse Events

An AE is any untoward medical occurrence in a clinical study participant, temporally associated with the use of study intervention, whether or not considered related to the study intervention. An AE can therefore be any unfavorable and unintended sign (including an abnormal laboratory finding), symptom, or disease (new or exacerbated) temporally associated with the use of study intervention. AEs will also be evaluated by the investigator for the coexistence of MAAE which is defined as an AE that leads to an unscheduled visit to a healthcare practitioner (HCP).

For analysis purpose, an AE is defined as any event occurring during the study but not present before exposure to study vaccine. Worsening of a pre-existing condition after vaccination will be reported as a new AE.

An unsolicited AE is any AE reported by the participant that is not specified as a solicited AR in the protocol or is specified as a solicited AR but starts outside the protocol-defined period for

reporting solicited ARs (i.e., 7 days after each study injection). For analysis and reporting purpose, unsolicited AEs will include the following:

- AEs that are reported by participants and recorded on the AE eCRF
- Solicited ARs that meet SAE criteria or last beyond 7 days after each injection and are recorded on the Reactogenicity eCRF

Unsolicited AEs will be collected for up to 21 days after each injection; SAEs, MAAEs, AESIs, and AEs leading to study discontinuation will be collected throughout the study. Unsolicited AEs will be summarized up to 21 days separately after Day 1 injection and Day 22 injection unless otherwise specified. Additionally, SAEs, MAAEs, AESIs and AEs leading to study discontinuation will be summarized throughout the study (up to Day 202/EoS). Refer to Safety Estimand 3b in Appendix G, Table 6.

All summary tables (except for the overall summary of AEs) for unsolicited AEs will be presented by SOC and PT (or by PT). SOC will be displayed in internationally agreed order. PTs will be displayed in descending order of frequency in the "D1: Fluzone HD+mRNA-1345 (pug) and D22: placebo" group and then alphabetically within SOC. When summarizing the number and percentage of participants with an event, participants with multiple occurrences of the same AE or a continuing AE will be counted once.

For the by-severity summaries, the toxicity grade of a solicited AR meeting SAE criteria or lasting beyond 7 days after each injection will be mapped to a severity level of Mild/Grade 1, Moderate/Grade 2 or Severe/ \geq Grade 3 and the maximum severity level in the case of multiple events will be presented.

Percentages will be based upon the number of participants in the Safety Set within each treatment group.

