5.4. Criteria for Temporarily Delaying the Administration of Study Intervention

Body temperature (oral preferred) must be measured on the study intervention visit before dosing. The following events constitute criteria for delay of study intervention dosing, and if any of these events occur at the time scheduled for dosing, the participant may receive the study intervention dosing at a later date within the time window specified in the SoA (Table 1), or the participant may be discontinued from dosing at the discretion of the Investigator (Section 7):

- Acute moderate or severe infection with or without fever at the time of study intervention dosing.
- Fever, defined as body temperature ≥38.0°C/≥100.4°F at the time of study intervention dosing.

Participants may be contacted within the time window acceptable for participation and re-evaluated for eligibility. If the Investigator determines that the participant's health on the day of dosing temporarily precludes study intervention, the visit should be rescheduled within the allowed interval for that visit.

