7.1. Discontinuation of Study Intervention

In rare instances, it may be necessary for a participant to permanently discontinue study intervention. If study intervention is permanently discontinued, the participant should, if at all possible, remain in the study for follow-up and for any further evaluations that need to be completed (see the SoA [Table 1]).

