5.4. Safety Set

The Safety Set includes all randomized participants who receive any study intervention.

The Safety Set will be used for all analyses of safety data except for the solicited ARs. Participants will be included in the treatment group corresponding to the study intervention they actually received.

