- b) Study day on or after the date of the Day 1 injection but before the Day 22 injection (if applicable) will be calculated as: date of assessment/event date of the Day 1 injection + 1;
- c) Study day on or after the date of the Day 22 injection will be calculated as: date of assessment/event date of the Day 22 injection + 1; if study day is on the same day as the Day 22 injection, date and time will be compared with the Day 22 injection date and time. If it is prior to the Day 22 injection, then study day is calculated as bullet point b); if it is after the Day 22 injection or the time is missing or not available then study day is calculated as: date of assessment/event date of the Day 22 injection + 1.

For GMT and GMC calculation, antibody values reported as below the LLOQ will be replaced by $0.5 \times \text{LLOQ}$ and antibody values greater than the ULOQ will be converted to the ULOQ.

Unscheduled visits: Unscheduled visit measurements will be included in analysis as follows:

- In the derivation of baseline measurements.
- In scheduled visit windows per specified visit windowing rules.
- In individual participant data listings as appropriate.

Visit windowing rules: The analysis visit windows for protocol-defined visits are provided in Appendix B.

Incomplete/missing data:

- Imputation rules for missing dates of prior/concomitant medications and non-study vaccinations are provided in Appendix C.
- Imputation rules for missing dates of prior/concomitant procedures are provided in Appendix D.
- Imputation rules for missing AE dates are provided in Appendix E.
- Other incomplete/missing data will not be imputed, unless specified otherwise.

Treatment groups:

The following treatment groups will be used for summary purposes:

- D1: Fluzone HD+mRNA-1345 (μg) and D22: placebo
- D1: Fluzone HD+placebo and D22: mRNA-1345 (μg)

If a subject receives any dose of mRNA-1345 on Day 1, regardless of the treatment group the subject is randomized to, the subject will be included in the actual treatment group "D1: Fluzone HD+mRNA-1345 (µg) and D22: placebo" for safety and reactogenicity analyses.

All analyses and data summaries/displays for disposition, demographics and baseline characteristics, safety and immunogenicity will be provided by treatment group using appropriate analysis population, unless otherwise specified. Local solicited adverse reactions will be also summarized by injection content (mRNA-1345, Placebo and Fluzone HD).

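### Unsolicited AE percentages after the Day 22 injection use the full Safety Set, which counts participants who never received that injection

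*SAP*

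**What the plan says.** SAP section 6.3.2 sets the reporting periods: "Unsolicited AEs will be summarized up to 21 days separately after Day 1 injection and Day 22 injection unless otherwise specified". For the denominator it says "Percentages will be based upon the number of participants in the Safety Set within each treatment group". SAP section 5.4 defines that set: "The Safety Set includes all randomized participants who receive any study intervention". One injection visit is enough to qualify.

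SAP section 6.1 fixes how events are assigned to an injection. For events "on or after the date of the Day 1 injection but before the Day 22 injection (if applicable", days are counted from Day 1. The next rule begins "Study day on or after the date of the Day 22 injection will be calculated as" and counts from the Day 22 injection itself.

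Both documents expect some participants to miss the second injection. SAP section 6.2.1 has a disposition row for them: "Prematurely discontinued before receiving the Day 22 injection and the reason for discontinuation". Protocol section 5.4 lets a delayed dose be given later within the window, "or the participant may be discontinued from dosing at the discretion of the Investigator". Protocol section 7.1 adds: "If study intervention is permanently discontinued, the participant should, if at all possible, remain in the study for follow-up".

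For solicited reactions the SAP does otherwise. Section 5.5 defines a Day 22 Solicited Safety Set limited to participants who had the Day 22 injection and contributed diary data after it, and section 6.3.1 uses it for the post-Day 22 tables.

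**The concern.** Unsolicited AEs in the 21 days after each injection are a primary safety endpoint, and a reader will take a post-Day 22 percentage as the rate among people given that injection. Under the stated denominator it is the proportion of everyone injected at least once, which is never higher and is lower whenever someone missed the injection.

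The figure most exposed is Arm 2 after Day 22. That is the only place in the trial where mRNA-1345 is given without Fluzone HD on the same day, so it is the natural reference for tolerability of the RSV vaccine alone. If the share who missed Day 22 also differed between arms, the between-arm comparison in these tables would shift slightly for reasons unrelated to safety.

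**Working it through.** **The plan's own safety figure.** SAP section 4.3 gives about 95% probability of seeing at least one participant with an AE at a true rate of 0.3%, with 950 per group. Check: 1 - (1 - 0.003)^950 = 94.2%. This reproduces, and it is a per-arm statement for the whole group.

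**Can a non-recipient enter the numerator?** Take a participant who missed the Day 22 injection and has an AE on Day 30. Under SAP section 6.1 the most recent injection is the Day 1 injection, so the event is on study day 30 and lies outside the 21-day window. No post-Day 22 window exists for this participant. He or she adds 0 to the numerator and 1 to the denominator.

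**Does anything override the denominator?** The general rule in SAP section 6.1 allows exceptions. None appears in sections 6.3.2.1 to 6.3.2.6 or in Safety Estimand 3b (Appendix G, Table 6).

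**Formula.** Let N be the Safety Set in an arm, m the share without the Day 22 injection, and r the rate among recipients. Reported percentage = r × N(1 - m) / N = r(1 - m). Example with N = 950 and m = 2%: 931 recipients; 0.20 × 931 / 950 = 19.6%.

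**Size.** Neither m nor the AE rate is in the documents. All values of both below are assumptions.

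| Assumed m | 950 × (1 - m) | True 10% reads | True 20% reads | True 20% vs 15%, same m: difference reads |
|---|---|---|---|---|
| 1% | 940.5 | 9.9% | 19.8% | 4.95 points |
| 2% | 931 | 9.8% | 19.6% | 4.90 points |
| 5% | 902.5 | 9.5% | 19.0% | 4.75 points |
| 10% | 855 | 9.0% | 18.0% | 4.50 points |

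With the same m in both arms the ratio is unchanged: 0.20(1 - m) / [0.15(1 - m)] = 1.33.

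**Unequal m (illustration only).** With a true 20% in both arms and m of 5% in one and 2% in the other, the arms read 0.20 × 0.95 = 19.0% and 0.20 × 0.98 = 19.6%. That is an artificial gap of 0.6 points, ratio 0.98 / 0.95 = 1.03. The 95% half-width for a difference at 20% with 950 per arm is 1.96 × sqrt(2 × 0.2 × 0.8 / 950) = 3.6 points, so the gap is well inside sampling error.

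**The 1% cut-off table (SAP section 6.3.2.4).** On 950, a preferred term needs 10 participants, since 9 / 950 = 0.95%. On Day 22 recipients, 9 suffice only once the denominator is 900 or fewer (9 / 900 = 1.00%). That takes at least 50 missed injections of 950, or m of 5.3%.

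**Tables not affected.** Post-Day 1 summaries, whole-study summaries, summaries counted after any injection, and solicited reactions.

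**The case against.** The strongest reply is that the denominator is a declared choice. Protocol section 9.5.2 and SAP sections 5.4, 6.3 and 6.3.2 agree on it. Safety Estimand 3b targets everyone receiving any study intervention and applies a treatment-policy strategy, so the reported proportion matches the declared estimand. That stands: this is not an internal contradiction. But treatment policy keeps the data collected, and no data can exist after an injection that was not given. The declared quantity is simply not the rate that an after-injection table appears to show.

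A second reply is that the missing count is already planned. SAP section 6.2.6 tabulates Day 22 recipients by group for the Safety Set, and section 6.2.1 does so in the disposition table. That also stands. Overall percentages need one division, though the reader must repeat it for each row of each table.

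Third, the solicited-reaction subset also requires diary data, so it is partly a data-availability set. True, but it shows that the SAP can already restrict a post-Day 22 table to recipients.

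Three stronger readings are tempting, and the documents support none of them:

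- **That 10% is a ceiling for m,** because the plan assumes about 10% ineligible for the PP Set and Estimand 1a refers to the dose on both days. The 10% is an approximate planning figure for the PP Set, not a bound on missed injections. The illustrative exclusion list in SAP section 6.2.7 names a wrong injection, not a missed one. Estimand 1a keeps data from early discontinuations, and Arm 1's Day 22 blood is drawn before the Day 22 dose.
- **That the arms will differ in m.** Only Arm 1 gets mRNA-1345 on Day 1, Protocol section 2.2 reports more solicited reactions with it than with placebo, and Protocol section 7.2 lists reactogenicity as a withdrawal reason. Yet section 2.2 also describes mostly Grade 1 or 2 reactions that resolved in 1 to 2 days, and the withdrawal list looks generic. No figure by arm is given.
- **That the SMQ and HLGT tables are understated too.** SAP section 6.3.2.5 plans numbers of events and participants, and section 6.3.2.6 mentions no percentages.

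**Conclusion.** The point holds as a minor one. Post-Day 22 unsolicited AE percentages equal the rate among recipients times (1 - m), so they are understated in relative terms by exactly m. The understatement of a true 20% is 0.2 to 2.0 points over the assumed range of 1% to 10%. The direction follows from the SAP's definitions, provided at least one participant misses the Day 22 injection; the size rests wholly on the assumed m.

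No safety hypothesis is tested, and sample size, power and type I error are untouched. A reader might infer a biased safety comparison between arms. The documents do not support that: with the same m the ratio is exact, unequal m is not shown, and the illustrated gap is about one sixth of the sampling half-width (0.6 / 3.6). The case for acting is that the correction is cheap and the endpoint is primary, not that the distortion is large.

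**What to change.** Define a Day 22-injected subset of the Safety Set, parallel to the Day 22 Solicited Safety Set in SAP section 5.5. Use it as the denominator wherever post-Day 22-injection AE percentages are shown: the overview, SOC/PT, PT, severity and 1% cut-off tables, and any optional subgroup versions. Keep the full Safety Set for Day 1 and whole-study tables. Align SAP sections 5.4, 6.3 and 6.3.2 and the population wording of Estimand 3b, and list the departure from Protocol section 9.5.2 in SAP section 7.

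A smaller step is to print the number of Day 22 recipients in the header of each post-Day 22 AE table. The table shells are not among the documents, so they may already do this.

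**Cost.** One population flag, the wording changes and one section 7 entry; no new data. Day 1 and Day 22 AE tables will have different denominators, which needs a footnote. The subset is defined after randomization, so between-arm comparisons in it are descriptive only. The numerators of these tables already come from Day 22 recipients alone.
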